5. TRIAL AIM

Assessment of the efficacy and safety of single-bolus intravenous injection of Fortelyzin® in comparison with bolus infusion of Actilyse® in patients with ischemic stroke.

6. TRIAL OBJECTIVES

- To assess the efficacy of single-bolus intravenous injection of Fortelyzin® in comparison with bolus infusion of Actilyse® in patients with ischemic stroke.
- To assess the safety and possible adverse events of single-bolus intravenous injection of Fortelyzin® in comparison with bolus infusion of Actilyse® in patients with ischemic stroke.

7. TRIAL POPULATION

Description of the trial population

This trial is planned to involve adult patients of both sexes aged 18 years and older with a verified diagnosis of ischemic stroke.

7.1. Inclusion criteria

- Men and women aged 18-80 (inclusive) years old.
- Verified diagnosis of ischemic stroke (neuroimaging (CT/MRI) signs of ischemic stroke, from 5 to 25 points on the NIHSS scale).
- Duration of symptoms of ischemic stroke is not more than 4.5 hours before starting thrombolytic therapy.
- The patient's consent to use reliable contraceptive methods throughout the trial and within 3 weeks after:
 - women who have a negative pregnancy test and use the following means of contraception: intrauterine devices, oral contraceptives, a contraceptive patch, long-acting injectable contraceptives, a double-barrier method of contraception. Women who are not at risk of pregnancy for health-related reasons (documented conditions: hysterectomy, tubal ligation, infertility, menopause for more than 1 year) may also be involved in the trial.);
 - men who use barrier contraception. Men who unable to fertilize (documented conditions: vasectomy, infertility) may also be involved in the trial.
- A participant provided signed and dated informed consent of participation in the trial.

7.2. Exclusion criteria

- The time of the onset of the first symptoms is more than 4.5 hours from the onset of the disease or the time of the onset of the first symptoms of a stroke is not known (for example, the development of a stroke during sleep - the so-called "night stroke").

- Increased sensitivity to alteplase, gentamicin (residual traces from the production process).
- Systolic blood pressure greater than 185 mm Hg or diastolic blood pressure greater than 110 mm Hg or the need for intravenous administration of drugs to reduce the blood pressure to these boundaries.
- Neuroimaging (CT, MRI) signs of intracranial hemorrhage, brain tumors, arteriovenous malformation, brain abscess, aneurysm of cerebral vessels.
- Surgery on the brain or spinal cord.
- Suspicion of subarachnoid hemorrhage.
- Signs of severe stroke: clinical signs (stroke scale NIH > 25), neuroimaging (according to CT of the brain and/or MRI of the brain in the DWI, the ischemia focuses on the territory of more than 1/3 of the MA pool).
- Simultaneous administration of oral anticoagulants, for example, warfarin with INR > 1.3.
- The use of direct anticoagulants (heparin, heparinoids) in the 48 hours preceding the stroke with APTT values above the norm.
- Prior stroke or severe head injury within 3 months.
- Significant regression of neurological symptoms during the observation of the patient
- Light neurological symptoms (NIH < 4 points)
- Hemorrhagic stroke or stroke, unspecified in history.
- Strokes of any genesis in the history of a patient with diabetes mellitus.
- Gastrointestinal bleeding or bleeding from the genitourinary system in the last 3 weeks. Confirmed exacerbations of gastric ulcer and duodenal ulcer during the last 3 months.
- Extensive bleeding, present or within the previous 6 months.

- Severe liver disease, including liver failure, cirrhosis, portal hypertension (with varicose veins of the esophagus), active hepatitis.
- Acute pancreatitis.
- Bacterial endocarditis, pericarditis.
- Aneurysms of arteries, malformations of arteries and veins. Suspicion of exfoliating aortic aneurysm.
- Neoplasms with an increased risk of bleeding.
- Large operations or severe injuries within the last 14 days, minor surgery or invasive manipulation in the last 10 days.
- Puncture of uncompensated arteries and veins during the last 7 days.
- Prolonged or traumatic cardiopulmonary resuscitation (more than 2 min).
- Pregnancy, obstetrics, 10 days after delivery.
- The number of platelets is less than 100,000/ μ L.
- Blood glucose less than 2.8 mmol/l or more than 22,5 mmol/l.
- Hemorrhagic diathesis, including renal and hepatic insufficiency.
- Data on bleeding or acute trauma at the time of examination.
- Seizures in the onset of the disease, if there is no certainty that the seizure is a clinical manifestation of ischemic stroke with a postictal residual deficiency.

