– a bolus and bolus+infusion i.v. injection of Fortelyzin® at a dose of 10 mg in comparison with Actilyse® in patients with acute myocardial infarction with ST-segment elevation (STEMI) showed the efficacy of the study drug comparable to that of Actilyse®;

– it is recommended to increase the dose of Fortelyzin® to 15 mg, administered according to the two schemes: the first scheme: 10 mg bolus + 5 mg bolus with an interval of 30 minutes; the second one: 10 mg bolus + 5 mg infusion for 30 minutes.

The further study assessed a bolus and bolus-infusion of Fortelyzin® at a dose of 15 mg vs. Actilyse® according to the Protocol "An open-label, prospective study of tolerability and efficacy of Fortelyzin® vs. Actilyse® in patients with acute myocardial infarction (phase III)", the authorization of Roszdravnadzor No. 196 dated 28.04.2010.

A total of 90 people were screened in 6 clinics, and 41 patients in the Fortelyzin® study group and 13 patients in the Actilyse® study group were included in the study.

In the Fortelyzin® group, a combination of bolus + infusion was administered to 21 patients, and 20 patients received a double bolus dose.

Assessment of the tolerability of the study drug revealed no serious adverse events (SAE) or hemorrhagic stroke in any of the groups observed. There was one adverse event in the form of "no-reflow" syndrome in the Fortelyzin® group and one bleeding in the Fortelyzin® group (considered as not related to the drug administration) and in the Actilyse® group (related to the drug administration).

There were no allergic reactions, nausea, and vomiting after administration of the drugs in both groups of patients. The maximum drop in blood fibrinogen on the first day after administration of Actilyse® was 38 %, and after administration of Fortelyzin® - only 7 %. The difference is statistically significant.

There was no decrease in blood pressure, increased pulse, and heart rate in both groups of patients.

Thus, the clinical study of bolus and bolus+infusion administration of Fortelyzin® showed their comparable tolerability with Actilyse® in STEMI patients.

Direct and indirect methods were used to assess the blood flow through the coronary arteries.

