4. Signs of a severe stroke: clinical [score on the National Institutes of Health Stroke Scale (NIHSS) > 25], neuroimaging (based on CT of the brain and/or MRI of the brain in the diffusion-weighted imaging (DWI) mode, the focus of ischemia extends to the territory of more than 1/3 of the CMA pool)
5. Seizures in the onset of the disease, if there is no certainty that the seizure is a clinical manifestation of ischemic stroke with a postictal residual deficiency
6. Previous stroke or severe traumatic brain injury within 3 months
7. Stroke of any genesis in the history combined with diabetes mellitus
8. Suspected subarachnoid hemorrhage (SAH)
9. Surgical intervention on the brain or spinal cord in the anamnesis

Cerebral and somatic

10. Arterial aneurysms, defects in the development of arteries or veins
11. Tumors with a high risk of bleeding

Somatic

12. Hypersensitivity to any component of the drug
13. Hemorrhagic diathesis

14. Arterial hypertension greater than 185/105 mm Hg or the need for intensive reduction below these figures
15. Bacterial endocarditis, pericarditis
16. Gastrointestinal bleeding or bleeding from the genitourinary system in the last 3 weeks. Confirmed exacerbations of gastric ulcer and duodenal ulcer during the last 3 months.
17. Liver failure (cirrhosis, active hepatitis, portal hypertension)
18. Acute pancreatitis
19. Present bleeding or extensive bleeding in the last 6 months
20. Extensive surgery, trauma, delivery, puncture of non-compressible vessels, cardiopulmonary resuscitation within the last 10 days
21. Pregnancy. Before the study, women of childbearing age will be asked to have a urine pregnancy test (determination of chorionic gonadotropin (HCG) in the urine).
22. Data on bleeding or acute injury at the time of examination.

Laboratory

23. Administration of warfarin and INR > 1,3
24. Use of heparin for 48 hours with increased aPTT
25. Thrombocytopenia less than 100,000/ μ l
26. Glycemia less than 2.8 and more than 22.5 mmol/l

Posology and method of administration

For Intravenous Use Only!

Fortelyzin® is administered intravenously as early as possible from the onset of clinical symptoms, but no later than 4.5 hours from its onset. The content of each of the two vials of 5 mg (745,000 IU) is diluted in 5 ml of isotonic sodium chloride solution. Fortelyzin® administered intravenously as a bolus dose of 10 mg for 5-10 s. The solution should be prepared immediately before use and should not be stored.

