7.4. Criteria for early termination of trial participants

A patient should be withdrawn from the trial immediately after any of the following situations occur:

- a patient or his/her legal representative or attending physician sends a request to exclude the patient from the trial, based on the withdrawal of Informed Consent (the patient's unwillingness to continue participation in the trial);
- pregnancy;
- significant violation of the Protocol procedures;

The reason for each unscheduled termination should be noted in the Case Report Form (CRF) in the section "Trial Completion". Follow-up will be performed for all patients who have dropped out of the trial due to adverse events or other safety parameters.

Follow-up will also be performed for all patients who have dropped out of the trial for other reasons, but also experience adverse events or have other safety parameters that might lead to discontinuation of therapy. In the case of early termination, the treatment of the underlying disease continues in accordance with recommendations and health standards.

Follow-up should be continued until the patient's condition is restored; until the diagnosis of an adverse event or a change in the safety parameter is stabilized or established chronically; as long as there are clinical indications for follow-up, or the duration of follow-up is determined by an attending physician-investigator.

In the case of pregnancy, every effort should be made to fully monitor the course of pregnancy until the moment of delivery, and child growth.

Randomized patients who did not complete the trial for reasons including those related to the trial drug will be included in the analysis of efficacy and safety data. Replacement of the removed randomized patients with newly included ones is not provided.

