9. TRIAL PROCEDURES

Visit 1 (Start of the trial)

Prior to administration of the trial drug, all patients will undergo the following procedures:

- determination of inclusion/non-inclusion criteria
- signing of Informed consent
- collection of demographic data (date of birth, sex)
- collection of medical history (duration of the underlying disease, previous therapy, allergological anamnesis, etc.)
- physical examination
- evaluation of changes by organs and systems
- assessment of neurological status using the NIHSS and modified Rankin scales (mRS)
- Duplex scanning of the major arteries of the head (if necessary)
- CT/MRI examination of the brain
- assessment of CT changes according to ASPECTS (Alberta Stroke Program Early CT Score)
- angiography of the cerebral vessels (if necessary)
- blood sampling for hematological and biochemical analyses
- coagulogram
- common urine analysis
- ECG
- assessment of the patient's compliance with the inclusion/exclusion criteria
- randomization

Assignment of individual patient identification code (IPIC)

The Investigator must ensure the anonymity of the trial subjects. The full names of all patients participated in the trial are strictly confidential.

After signing the Informed Consent Form, each patient will be assigned an Individual Patient Identification Code (IPIC) in accordance with the current legislation (Table 6).

Table 6. Individual Patient Identification Code

Permission of the Ministry of Health of the Russian Federation No.	Permission's date of issue, DD/MM/YYYY/	Serial number of the medical organization specified in the Permission	Patient's initials	Patient's date of birth, DD/MM/YYYY/	A unique number assigned to the patient by the Investigator, consisting of letters and numbers (the name of the protocol and the screening number under which the patient was included in the trial)
--	---	---	--------------------	--------------------------------------	--

The individual patient identification code (IPIC) is established by the Insurant based on the patient data provided by the Investigator. The individual patient identification code is reported by the Insurant to the Investigator for inclusion in his medical documentation. The IPIC will be reflected in the primary documentation, Case Report Form, and Patient Information Sheet with the informed consent form. The IPIC will be transmitted by the Code Registry by the Insurant to the Insurer.

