10. THERAPY DURING THE TRIAL

Study drug: Fortelyzin®

Manufacturer: Supergene, LLC, Russia

Drug description

Pharmaceutical form: lyophilizate for preparation of a solution for intravenous administration, supplied with a solvent

Detailed description:

Lyophilizate: tablet-like freeze-dried mass of white or almost white color.

Solvent: colorless transparent liquid.

Reconstituted solution: colorless, transparent or slightly opalescent liquid.

Composition:

Active substance: Forteplase® (recombinant protein containing the amino acid sequence of staphylokinase) 5 mg (745,000 IU).

Excipients: L-arginine - 15,0 mg, L-histidine - 2,0 mg, glycine - 30,0 mg, povidone - 17:20,0 mg, polysorbate -20:0,4 mg.

Solvent: 5mL ampule of sodium chloride 0.9% solution for injection

Dosage regimen: Fortelyzin® will be assigned at a dose of 10 mg (1,490,000 IU).

Route of administration: intravenously in the form of a single bolus injection for 5-10 sec. The solution of Fortelyzin® is prepared immediately before administration: the content of a 5 mg vial (745,000 IU) is diluted in 5 ml of 0.9% sodium chloride solution. Non-storable!

Labeling: «Product for clinical trial only».

Active Comparator: Actilyse®

Manufacturer: Boehringer Ingelheim Pharma GmbH & Co. KG

Drug description

Pharmaceutical form: lyophilizate for preparation of a solution for infusion supplied with a solvent.

Detailed description:

Lyophilizate: freeze-dried mass of white or light yellow color.

Solvent: colorless transparent liquid

Composition:

Active substance: Alteplase 50,0 mg

Excipients: L-arginine: 1742.0 mg,

Phosphoric acid, 85 %: up to pH 7.2 ± 0.2,

Polysorbate 80: 3.5-5.0 mg.

Note

The excess is 3.5 % of the nominal amount of the active ingredient and excipients in the vial.

Residual traces: gentamicin (used in the production process).

Each vial of solvent contains:

Water for injection: 50 ml

1 ml of the solution after dilution contains 1 mg of alteplase.

Dosage regimen:

Actilyse ® is administered in accordance with the instructions for use in ischemic stroke at a dose of 0.9 mg/kg, maximum 90 mg, if a patient's weight exceeds 55 kg:

- 10% of the dose is administered intravenously via a syringe for one minute (bolus);
- the main dose of the drug (90% of the dose) is administered within 60 minutes (using a syringe dispenser / infusomat);

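### The hypersensitivity exclusion names only Actilyse substances, so a patient for whom Section 2 contraindicates Fortelyzin is eligible and has a one-in-two chance of being allocated it

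*Combined protocol and SAP*

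**What the plan says.** Section 7.2 has one hypersensitivity criterion, "Increased sensitivity to alteplase, gentamicin (residual traces from the production process", and the Protocol Summary repeats it in the same words. None of the other inclusion or exclusion bullets (Sections 7.1 and 7.2) mentions allergy.

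Section 2 lists 26 contraindications to Fortelyzin. Item 12 is "Hypersensitivity to any component of the drug".

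Section 10 gives the composition of both products. For Fortelyzin: "Active substance: Forteplase® (recombinant protein containing the amino acid sequence of staphylokinase) 5 mg (745,000 IU" and "Excipients: L-arginine - 15,0 mg, L-histidine - 2,0 mg, glycine - 30,0 mg, povidone - 17:20,0 mg, polysorbate -20:0,4 mg". Gentamicin appears only in the Actilyse entry: "Residual traces: gentamicin (used in the production process".

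Section 9 (Visit 1) requires, before randomisation, "collection of medical history (duration of the underlying disease, previous therapy, allergological anamnesis, etc". The same list ends with the check against the inclusion and exclusion criteria, followed by randomisation. Under Section 8, allocation is to two equal groups of 168.

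**The concern.** In a randomised comparison every eligible patient must be able to receive either treatment. The list that decides eligibility should therefore contain the contraindications to both drugs. Here the allergy criterion protects patients from two Actilyse substances and from nothing in Fortelyzin, although the same protocol says that a patient allergic to any Fortelyzin component must not receive it.

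What is at stake is patient safety. Section 2 itself says that allergic reactions to Fortelyzin cannot be ruled out. Fortelyzin is given as a bolus over 5 to 10 seconds, so in practice the dose is complete before a reaction could prompt anyone to stop it, whereas the 60-minute Actilyse infusion can be interrupted. Prior exposure is also possible: Fortelyzin has been registered since December 2012, 1,531 STEMI patients were followed between June 2013 and June 2015, and earlier treatment with it is not an exclusion.

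The primary comparison is not in question. Section 7.4 says that randomised patients who do not complete "for reasons including those related to the trial drug will be included in the analysis of efficacy and safety data".

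**Working it through.** **1. Which components the exclusion covers.** The table sets the Section 7.2 bullet against the Section 10 compositions, leaving out the solvents.

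| Product | Components listed in Section 10 | Named in the exclusion |
|---|---|---|
| Fortelyzin | Forteplase, L-arginine, L-histidine, glycine, povidone-17, polysorbate-20 (1 + 5 = 6) | none (0 of 6) |
| Actilyse | alteplase, L-arginine, phosphoric acid, polysorbate 80, gentamicin traces (1 + 3 + 1 = 5) | alteplase, gentamicin (2 of 5) |

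The two named substances and the six Fortelyzin components have no member in common.

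**2. Whether another criterion closes the gap.** The 26 contraindications in Section 2 can be set against Section 7.2 one by one. Each of the other 25 has a matching exclusion bullet, although some limits differ (for example, diastolic pressure is 105 mm Hg in Section 2 and 110 mm Hg in Section 7.2). Item 12 is the only one whose counterpart does not refer to Fortelyzin. No reason is given, and this looks like an oversight.

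**3. Probability of allocation.** From Section 8, 168/336 = 0.5.

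**4. Expected numbers.** The documents do not say how many stroke patients have a known allergy to a Fortelyzin component. Let p be that proportion. Then the expected number admitted is 336 × p, and the expected number allocated to Fortelyzin is 336 × p × 0.5.

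| Assumed p | Admitted | Allocated to Fortelyzin |
|---|---|---|
| 0.1% | 336 × 0.001 = 0.34 | 0.17 |
| 0.5% | 336 × 0.005 = 1.68 | 0.84 |
| 1% | 336 × 0.01 = 3.36 | 1.68 |

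The range for p is an assumption, with no figure in the documents behind either end.

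**5. Shared and Actilyse-only excipients.** L-arginine is in both products, so a patient allergic to it would be exposed in either arm. A patient allergic only to polysorbate 80 or phosphoric acid would be exposed only in the Actilyse arm. The present wording covers neither case.

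**6. Sample size.** The Section 17 calculation uses the response proportions, margin, error rates and dropout. None of these depends on this bullet, and exclusion comes before randomisation, so the planned 336 stands.

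**The case against.** The strongest reply is that the protocol has partial safeguards. Item 12 is in the same document, an allergy history is taken before dosing, and the trial is open-label, so an investigator who learns of an allergy knows which drug was drawn and has a written statement against giving it. A one-in-two chance of allocation is therefore not a one-in-two chance of being dosed despite a known allergy. That distinction stands. But Visit 1 calls for a check against the eligibility criteria, not against Section 2. An investigator who notices only after allocation must choose between the allocation and the contraindication, and Section 7.4 has no withdrawal criterion for that situation and does not allow replacement. Section 3 does speak of selecting patients with all contraindications in mind, but that sentence concerns bleeding and is not an eligibility rule.

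A second reply is that the numbers are soft, and this is right. The prevalence range has no anchor in the documents, and the upper end should carry little weight. The component count shows what the wording omits; it does not measure risk, since three of the six Fortelyzin components are amino acids. The earlier myocardial infarction study reported that "There were no allergic reactions, nausea, and vomiting after administration of the drugs in both groups of patients", but this concerns reactions after dosing in 41 Fortelyzin and 13 Actilyse patients. It does not show how many stroke patients arrive with a known allergy. Even for reactions after dosing, zero in 41 is compatible with a rate up to 1 − 0.05^(1/41), or about 7% (one-sided 95% exact bound).

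Finally, the benefit of a change is limited. Some patients cannot give a history and have no representative (Section 4.2), and better wording would not help them. Section 10 already permits glucocorticoids and antihistamines for allergic reactions during thrombolysis. Both points are fair, but treating a reaction does not replace avoiding a known one.

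**Conclusion.** The concern holds. As written, the eligibility rule admits a patient whom Section 2 says must not receive one of the two randomised drugs. The textual mismatch is certain. Its practical size is not: the event is probably rare, and the figures of 0.3 to 3.4 patients admitted and 0.2 to 1.7 allocated to Fortelyzin rest wholly on an assumed prevalence of 0.1% to 1%. They also count allocation, not actual dosing. No estimand, error rate, sample size or analysis is affected. The correction should be made because it concerns patient safety, the information needed is already collected before allocation, and the cost is close to nil.

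**What to change.** Replace the bullet in Section 7.2 and in the Protocol Summary with: *Hypersensitivity to alteplase, gentamicin, Forteplase/staphylokinase, or any component (including excipients) of either trial drug.* State that it is checked against the Visit 1 allergy history before randomisation.

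The cost is one bullet reworded in two places, with no new procedure and no change to the planned 336. The only downside is a small number of additional exclusions: about 0.3 to 3.4 per 336 for Fortelyzin components under the same assumed prevalence, plus any patient allergic only to an unlisted Actilyse excipient.
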